6. GENERAL ANALYSIS DEFINITIONS

6.1 TREATMENT(S)

This is an open-label, non-randomized, phase I dose escalation and dose expansion study. In phase 1b four CRC cohorts are randomized and a single arm PDAC cohort. For the main analysis the phase 1a and phase 1b data will be pooled together.

The following "analyzing treatment" (Table 6.1:1) will be used for reporting treatment emergent adverse events (AEs) and safety laboratory variables and the timeline criteria "start date \leq onset date of AE < stop date" will be used to determine if an AE will be assigned to be "analyzing treatment" or not. Detailed rule for assigning AEs to these time periods are listed below:

- If the date of informed consent ≤ AE onset date < date/time of the first administration of BI 905711, then the AE is assigned to "Screening";
- If the date/time of the first administration of BI 905711 ≤ AE onset date < min{date of the late administration of BI 905711 + 35 days, DBL date}, then the AE is assigned to "On-treatment";
- If AE onset date ≥ date of the last administration of BI 905711 + 35 days, then the AE is assigned to "Follow-up".

AEs that have onset date during the screening or follow-up periods will be displayed in separate subject listings from those occurred during the on-treatment period. For the ontreatment and follow-up periods, AE frequency tabulations will contain a "total" column, representing all doses of BI 905711. Subject data listings of AEs will not have a "total" column. To justify the MTD determination, DLTs occurring during the MTD evaluation period and the entire on-treatment period will be displayed separately.

Table 6.1:1 Analyzing Treatments

Analyzing Treatment Period	Start Date (including) Stop Date (excluding)		
Screening	Data of informed consent	Date of the first administration of BI 905711	
On-treatment	Date of the first administration of BI 905711	Date of the last administration of BI905711 + 35 days (for discontinued patients); or DBL date (for on-going patients)	
Follow-up	Date of the last administration of BI 905711 + 35 days Note: on-going patients do not have follow-up periods	Date of the last per protocol visit or DBL date, whichever comes first	

MTD evaluation period	Date of the first administration of BI 905711	Date of the second administration of study BI 905711 + 35 days; or DBL date; or the start date of the third treatment cycle, whichever is earlier
-----------------------	--	--

Note: a 35-day residual effect period is defined for this study. DBL = database lock. 29 days is from the criteria of DLT since any drug-related AE that causes a > 28 days of drug free interval is a DLT.

The actual treatment codes and decodes, the labels for the analyzing treatment, and the analysis numbers are defined in the technical TSAP document of ADS Plan and Data Guide and stored in the same location with this document in Boehringer Ingelheim Regulatory Documents for Submission (BIRDS).

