Vital Signs		X	X	X	X	X	Х		X			X	X		X	X	X	X			
Safety lab parameters ¹⁰		x	X	x ¹ 0		X	X		X			X	X		Х	X	X	X	X	X	
Pharmacokinetics ¹¹			Х	Х	Х	х	х	X	Х	Х	X	Х	Х	Х	Х		Х	X	X		
ADA sampling 11			X				X		X						X		Х	X	X		
Fresh tumor biopsy ¹²	x ^{12,18}	x ¹²						x ¹²										x ¹²			
Archival tumor tissue ¹²	x ^{12,18}	x ¹²																			
[¹⁸ F]FDG-PET/CT ¹³		x ¹³									2	x ¹³									
Adverse Events ¹⁴		X	X	X	X	X	X	X	X	X	+-	X	2	x x x	X	X	X	X	X		
Concomitant Therapy		X	X	X	X	X	X	X	X	X		X	7	x x x	. X	X	X	X	X		

Page 19 of 165

Proprietary confidential information © 2023 Boehringer Ingelheim International GmbH or one or more of its affiliated companies

FLOW CHART: PHASE IB- WEEKLY DOSING (CONT.) – No longer applicable per CTP v7.0

				Treatment Period					Post-Treatment												
Visit	SV1 ¹⁸	SV2 ¹⁸ / Screen		Cyc	le 1*	•	Cycle	e 2 *β	,	Cycl	le 3 *	εβ	Cycle		cycle 5, 7, 9	s (e.g.	Even cycles (e.g. 6, 8, 10, etc) *β	*	EOR ***	FU for PD‡	FU for survival status‡
Day (day range)	Any time before SV2	-28 - 1	1 (+3)	2	3	8 (± 3)	1 (+2)	3	1 (+2)	2	3	8 (± 3)	1 (+2)	2	1 (+2)	8 (± 3)	1 (+2)	Day 0-7 after last dose	30 (+5) days after last dose		
Tumor assessment by CT/MRI RECIST 1.1 ¹⁵		x ¹⁵											Х	15	•						
Tumor marker ¹⁶		x ¹⁶		x^{16}																	
Termination of study medication																		X			
Patient vital status																					X

^(*) Each treatment Cycle has a duration of 14 days

^(**) Patients who discontinue trial treatment prematurely should undergo the End of Treatment (EOT) visit as soon as possible. If assessments due at EOT are not completed, they may be performed at the 30-Day Safety FUP Visit.

^(***) The 30-Day Safety Followup visit is the End of Residual Effect Period visit (EOR) which must happen at the earliest 30 (+ 5) days after the last dose of treatment (see Section 6.2.3.2). ‡Additional follow-up visits for progression after the 30-Day safety follow-up visit will be performed for patients who discontinue for reasons other than progression or death. Follow-up continues until progression per the imaging schedule (see Section 5.1). The follow-up visits for survival status will be performed every 12 weeks (+/-7 days)(in person or by telephone) until death, lost to follow-up, withdrawal of consent, or end of the whole trial (see Section 6.2.3.3).

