Tumor assessment by CT/MRI RECIST 1.11	Per institutional practice				
Pregnancy test ²	Per institutional practice ⁶				
12-lead-ECG	Per institutional practice ⁶				
Body weight	X	х			
Administration of BI 905711 ³	X	X	X		
Adverse Events ⁴	X	Х	X	X	X
Concomitant therapy ⁵	x	х	X	X	X
Termination of study medication				X	

^(*) Each treatment Cycle has a duration of 14 days

^(**) Patients who discontinue trial treatment prematurely should undergo the End of Treatment (EOT) visit as soon as possible. If assessments due at EOT are not completed, they may be performed at the 30-Day Safety FUP Visit.

^(***) This combined visit is the End of Residual Effect Period visit (EOR) which must happen at the earliest 30 (+ 5) days after the last dose of treatment (see Section 6.2.3.2).

¹Tumor assessment will be performed according to institutional practices. Images no longer need to be sent to imaging vendor. Only overall response and disease progression will be collected in the electronic CRF.

²Serum and/or urine pregnancy testing to be performed for female patients of childbearing potential as per institutional practice.

³ Dispensing of BI 905711 will be performed via the IRT. Assessment for signs and symptoms of infusion-related reactions and Cytokine Release Syndrome (CRS) is described in Sections 4.1.4.1.1 and 4.1.4.1.2.

⁴ After the individual patient's end of trial: the investigator does not need to actively monitor for new AEs but should only report any occurrence of cancer of new histology, trial drug related SAEs and trial drug related AESIs of which the investigator may become aware of and only via the SAE form, see Section 5.2.6.2.1.

17Apr2023

Clinical Trial Protocol

Page 25 of 165

Proprietary confidential information © 2023 Boehringer Ingelheim International GmbH or one or more of its affiliated companies

Applicable to all patients ongoing patients:

After implementation of CTP v7.0, the patient will have assessments as medically indicated to monitor the safety at the discretion of the investigator. These assessments may include: physical examination, vital sign, safety lab and ECG at a frequency decided by the investigator. The study treatment is administered and the administration information will be documented in the eCRF. Tumour assessment will be performed according to standard of care based on medical opinion of the investigator.

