The molecular weight of BI 905711 is approximately 201 kDa, which is above the renal filtration cut-off threshold (approximately 60 kDa). Dedicated excretion studies were not conducted.

Pharmacokinetic drug interactions

BI 905711 is a therapeutic protein, and its clearance is through protein catabolism. BI 905711 is not an immune modulator and is not expected to impact expression and production of cytochrome P450 enzyme or certain drug transporters that may affect indirectly the exposure of co-administered small molecule drugs. Therefore, pharmacokinetic drug interaction between BI 905711 and co-administered small molecule drugs is not expected.

Residual Effect Period

The expected Residual Effect Period (REP) of BI 905711 is 30 days (+ 5 days). This is the period after the last dose with measurable drug levels and/or pharmacodynamic effects still likely to be present.

Proprietary confidential information © 2023 Boehringer Ingelheim International GmbH or one or more of its affiliated companies

Non-clinical studies

BI 905711 demonstrated high preclinical activity in-vitro and in-vivo for CDH17 positive tumor cell lines in extensive batteries of pre-clinical experiments fully described in the IB. A short summary is given below.

The sensitivity of a panel of 24 CDH17-positive colorectal cancer cell lines to BI 905711 treatment was evaluated and is shown in Figure1.2:1. A V-shaped dose-response is predicted for this bi-specific MoA where concentrations above the optimum will favor individual target recruitment, thus preventing TRAILR2 cross-linking and therefore reducing efficacy. Within the range of concentrations tested, different cell lines showed a reduced efficacy when using higher than optimal doses. Importantly, despite differences in CDH17 and TRAILR2 protein expression levels and the intrinsic sensitivity to TRAILR2 agonists among these cells, there was a common concentration range inducing the maximal effect for all of them (Figure 1.2: 1)

[figure not shown]

Figure 1.2: 1 Dose response graph of CRC cell lines classified as sensitive to BI 905711 as determined in the Cell Titer-Glo assay. Within the range of concentrations tested, different cell lines showed a V-shaped dose-response curve, and reduced efficacy was detected when using higher than optimal doses (c16856466).

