7.8.1 Adverse events

Adverse events will be coded using the Medical Dictionary for Drug Regulatory Activities (MedDRA). Standard BI summary tables and listings will be produced. All adverse events with an onset between start of treatment and end of the residual effect period (REP), a period of 35 days after the last dose of trial medication, will be assigned to the on-treatment period for evaluation.

All treated patients will be included in the safety analysis. In general, safety analyses will be descriptive in nature and will be based on BI standards. No hypothesis testing is planned.

Statistical analysis and reporting of adverse events will concentrate on treatment-emergent adverse events, i.e. all adverse events occurring between start of treatment and end of the residual effect period. Adverse events that start before first drug intake and deteriorate under treatment will also be considered as 'treatment-emergent.'

The analyses of adverse events (AE) will be descriptive in nature. All analyses of AEs will be based on the number of patients with AEs and not on the number of AEs. Frequency of patients with AEs will be tabulated by treatment dose, highest CTCAE grade, system organ class (SoC) and preferred term after coding according to the current version of MedDRA at the database lock. In addition, AEs will be tabulated by preferred terms only. The SoC will be sorted alphabetically. In tables displaying AEs by preferred terms, this will be sorted by descending frequency of AEs in the "Total" BI 905711 group.

Summary tables and listings of AEs, SAEs, related AEs, related SAEs, AEs of special interest, AEs leading to dose reduction, AEs leading to treatment discontinuation and AEs leading to deaths will be provided. In addition the number of DLTs in the MTD period and during the study will be provided.

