7.8.2 Laboratory data

The analysis of laboratory data will be descriptively in nature and will follow standard procedures. The analysis of laboratory data will use the same "analyzing treatments" as described for AEs, except for that the baseline laboratory values will be included in the "on treatment" period. Patients having at least one post-baseline laboratory value will be displayed in the descriptive analyses. Patients with missing CTCAE grade at baseline or no baseline value but with post-baseline value will be displayed in the category "Missing CTCAE grade at baseline".

Descriptive statistics, including change from baseline, frequency of patients with transitions relative to the references range, will be provided for laboratory assessments at scheduled visits. Data collected during potential unscheduled laboratory assessments will be listed. No post-study laboratory values will be considered. CTCAE grade for applicable laboratory parameters will be calculated according to CTCAE v5.0. The following outputs will be presented:

- Baseline, last value and difference from baseline
- Worst CTCAE grade experienced during the on-treatment period

- Transitions of the CTCAE grade from baseline to the worst lab values, from baseline to the last lab values, and from the worst to last values during the on-treatment period
- Possible clinically significant laboratory values
- Transitions for laboratory values without CTCAE grade based on reference ranges

Note: For calculating the change in CTCAE grade from baseline, patients with a CTCAE grade of -9 (no CTCAE grade defined) or CTCAE grade of -5 (overlapping reference ranges) will be treated as a CTCAE grade 0 for all analyses. In laboratory listings, the CTCAE grade is displayed as -9 and -5, respectively.

For Uric Acid, Hypokalemia, amylase, bicarbonate, eosinophils, glucose (high direction), INR of prothrombin time, lipase, methemoglobin, sodium (low direction) the CTCAE grade cannot always be assigned by the laboratory parameter itself as two different CTCAE grades have the same laboratory constellation, but are distinguished by additional clinical parameter. In this case a CTCAE grade of -1 will be assigned. These will not be considered for laboratory analyses. In laboratory listings, the CTCAE grade is displayed as -1, respectively.

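### SAP 6.1 ends the on-treatment period at day +34 after the last dose, one day short of the residual effect period, so an AE with onset on day +35 leaves the treatment-emergent outputs

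*SAP*

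**What the plan says.** **SAP 6.1, bullets.** An AE is on-treatment if its onset is on or after the first dose and strictly before last dose + 35 days (or database lock, if sooner). For later onsets: "If AE onset date ≥ date of the last administration of BI 905711 + 35 days, then the AE is assigned" to Follow-up.

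**SAP Table 6.1:1.** The on-treatment row stops at last dose + 35 days for discontinued patients, in a column whose dates are excluded. The Follow-up row starts at last dose + 35 and stops, again excluded, at the last per-protocol visit or database lock. The note under the table says "a 35-day residual effect period is defined for this study".

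**SAP 7.8.1.** AEs with onset up to the end of the residual effect period, described as "a period of 35 days after the last dose of trial medication, will be assigned to the on-treatment period for evaluation".

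**SAP 7.8.2.** Laboratory data use the same periods as AEs, with baseline added to on-treatment.

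**Protocol.** Section 1.2 gives a residual effect period of 30 days (+5). Section 7.3.4 assigns AEs with onset up to its end, 30 days (+ up to 5) after the last dose, to the on-treatment period. The flow-chart footnotes say that the EOR visit "must happen at the earliest 30 (+ 5) days after the last dose of treatment". Under v7.0, section 6.2.3.3 makes EOR the end of study.

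**The concern.** The residual effect period defines which AEs count as treatment-emergent, and EOR is the visit that closes it. The SAP has taken the outer limit of the protocol's window, 35 days, as its residual effect period for every patient. The strict inequality then leaves out the last day of that window. SAP 6.1 and SAP 7.8.1 describe the same boundary and, on an ordinary reading, disagree about day +35.

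SAP 6.1 also disagrees with itself. For a patient whose last per-protocol visit is EOR, the bullet and the table give different answers for a day +35 onset, so two programmers could each follow the section and produce different outputs.

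At stake are the treatment-emergent AE tables, including the Phase Ib secondary endpoint (number of patients with treatment-emergent AEs), which the abbreviated report retains. To a lesser extent, the on-treatment laboratory summaries are also affected.

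**Working it through.** The check is day counting, with the last dose as day 0.

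**Inputs**
- On-treatment: onset < 35 (SAP 6.1 bullet; Table 6.1:1, stop excluded).
- Follow-up, bullet: onset ≥ 35. Follow-up, table: 35 ≤ onset < v, where v is the day of the last per-protocol visit, if that precedes database lock.
- Stated residual effect period: 35 days (SAP 6.1 note and 7.8.1).
- Permitted EOR days: 30 to 35, that is 35 − 30 + 1 = 6 days (protocol 1.2, 6.2.3.2 and flow-chart footnotes).

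**1. Reproduce the stated 35 days.** The interval [0, 35) holds days 0 to 34. That is 35 days if the dosing day is counted and 34 days (+1 to +34) if only days after the dosing day are counted. The label is met only on the first count.

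**2. Classify the permitted EOR days.**

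| Day after last dose | 30 | 31 | 32 | 33 | 34 | 35 |
|---|---|---|---|---|---|---|
| SAP 6.1 as written (< 35) | On | On | On | On | On | not On |
| Inclusive boundary (≤ 35) | On | On | On | On | On | On |

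As written, 5 of 6 permitted days are on-treatment. With the inclusive boundary it is 6 of 6, and the period runs over days +1 to +35, which is 35 days after the dosing day. Only day +35 changes.

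**3. Onset or visit date?** SAP 6.1 assigns by onset date. EOR collects new AEs since the end-of-treatment visit (protocol 6.2.3.2). An AE reported at a day +35 visit with onset on day +33 has 33 < 35 and stays on-treatment. Only an onset dated day +35 moves.

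**4. The Follow-up row.** If EOR is the last per-protocol visit, on day v, the row holds max(0, v − 35) days. For v = 30, 31, 32, 33, 34 and 35 this is 0 each time. At v = 35 the interval is [35, 35); for smaller v the stop precedes the start. By the table a day +35 onset has no period, while the bullet sends it to Follow-up. Patients followed for progression or survival after EOR under earlier protocol versions can have v > 35, and for them the row is not empty.

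**5. Laboratory data.** A sample taken on day +35 falls outside on-treatment by the same rule. The v7.0 reduced schedules keep safety laboratory results in source documents and out of the eCRF, so only day +35 samples collected before v7.0 are involved.

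**6. The Phase Ib endpoint.** It counts patients, and SAP 7.8.1 also analyses patients with AEs rather than numbers of AEs. A day +35 onset changes the count only if the patient had no earlier treatment-emergent AE. In Phase Ia (protocol 1.2) 41 of 48 patients (85.4%) had at least one, leaving 7 of 48 (14.6%) with none.

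**The case against.** The best defence is that a half-open interval of 35 days is a legitimate convention. Counting the dosing day, [0, 35) is exactly 35 days, and 7.8.1 does not say in terms whether day +35 is included. The protocol's nominal period is 30 days with a tolerance, so the SAP already counts more than a 30-day rule would. Under the explicit bullet nothing is lost, because SAP 6.1 provides listings and frequency tabulations for Follow-up AEs.

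Much of this stands. The 35-day label is defensible on its own, and under-counting is relative to the outer limit of the window. It does not remove the mismatch: a period of 35 days after the last dose ordinarily runs to day +35, protocol 7.3.4 lets the period extend that far, and the bullet and table still disagree where EOR is the last visit.

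A reader might infer more than the documents support:
- *That AEs and laboratory values found at any in-window EOR visit are excluded.* They are not. Days +30 to +34 are covered, and AEs are assigned by onset date. Neither document says that an AE detected at EOR takes the visit date as its onset.
- *That 1/6 (17%) of EOR visits lose their AEs.* One in six is the share of permitted days. It would be the share of visits only under an assumed even spread, and a day +35 visit loses only same-day onsets.
- *That EOR laboratory values are dropped in general.* For v7.0 patients there are none in the eCRF to drop. The SAP 7.8.2 sentence "No post-study laboratory values will be considered" does not address day +35.

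**Conclusion.** The boundary is narrowly wrong as written. SAP 6.1 and Table 6.1:1 stop on-treatment at day +34, against a protocol window and a SAP 7.8.1 period that reach day +35. For patients whose last visit is EOR, the table also contradicts the bullet.

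The affected data are AEs with onset dated exactly day +35 and laboratory samples taken that day before v7.0. The documents do not say how many EOR visits fell on day +35 or how many such onsets exist, so the number cannot be computed. It is likely very small, and the effect on the patient-level endpoint is smaller still. All analyses are descriptive, so no test or decision rule is affected.

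The conclusion rests on reading 30 (+5) as allowing day +35 and on reading 7.8.1 as including it. The conflict between bullet and table does not depend on the second reading.

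**What to change.** In SAP 6.1, in both the bullets and Table 6.1:1:
- On-treatment: first dose ≤ onset ≤ last dose + 35 days. In the table this is an excluded stop date of last dose + 36. The database-lock cap can stay.
- Follow-up: onset > last dose + 35 days. Align the table's stop with the bullet, so that AEs recorded in the CRF after that day, up to the patient's end of trial, are assigned to Follow-up. The stop should not simply be deleted: after the patient's end of trial, protocol 5.2.6.2.1 sends reports to the SAE form and not the CRF.
- Apply the same bounds to the laboratory data that were collected (SAP 7.8.2).

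SAP 7.8.1 then needs at most a word to say that day +35 is included. The cost is one changed inequality in the text and in the derivation program, plus the matching table cells. No new data are needed.

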6.2 IMPORTANT PROTOCOL DEVIATION

According to (5), important safety protocol deviations (PDs) are those that potentially affect the rights or safety of study subjects. Important PDs (IPDs) are those that can potentially influence the primary outcome measure(s) for the respective patients in a way that is neither negligible nor in accordance with the study objectives.

Handling of iPDs in analysis is included in the DV domain specifications and stored within the trial master file (TMF) in the electronic document management system (EDMS). The final list of iPDs will be confirmed at the last report planning meeting (RPM) before the database lock for the primary analysis of the primary endpoint PFS (based on blinded central independent review).

Important PDs will be documented in the DV template domain with input from clinical. The DV template domain will then be sent to data management that will convert to a data base for analysis.

6.3 SUBJECT SETS ANALYSED

- Screened set: This patient set includes all subjects who have signed the informed consent. The screened set will be used for patient disposition tables.
- Treated set (TS): This includes all subjects who were dispensed study medication and were documented to have been treated with at least one dose of BI 905711. This TS is used for both safety and efficacy analyses.
- MTD evaluation set (MTDS): This includes all patients in the TS who were not replaced for the MTD determination. The MTDS is used for the primary analyses of DLTs and MTD determination. Rules for replacement of patients are defined in the CTP Section 3.3.4.4. The list of replaced patients will be provided by the Trial

Clinical Monitor no later than the last RPM and should be documented in the RPM minutes.

• Pharmacokinetic parameter analysis set (PKS): This includes all subjects in the treated set (TS) who provide at least one PK endpoint and was not excluded due to a protocol deviation relevant to the evaluation of PK or due to PK non-evaluability (as specified in the following subsection Pharmacokinetics). Descriptive and potential model based analyses of PK parameters will be based on the PKS.

All analyses on immunogenicity will be based on Treated set (TS).

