• For the initial two dose levels (dose levels of 0.02 mg/kg and 0.06 mg/kg), at least one CRC patient was required. In case patients have not experienced a DLT within the first two cycles, enrollment into a higher dose level occured. In case a DLT occured, the number of patients was increased to four patients per dose level, and BLRM was performed to determine the next escalation steps. At least one Japanese patient should be included in the additional three patients that are enrolled. Then, all subsequent dose levels consisted of at least four patients. For further dose-escalation steps (dose level of 0.2 mg/kg and above), four CRC patients were required. However, in the case that only three patients were evaluable (including one Japanese patient) and none experienced a DLT as defined in Section 5.2.6.1.5 within the MTD evaluation period, then dose escalation occured based on these three evaluable patients.

If DLTs were observed in the first two consecutive patients of a previously untested dose level, subsequent enrollment to this dose cohort was stopped. The BLRM was to be re-run to confirm whether the dose level still fulfils the EWOC criterion. Based on this information, the SMC evaluated whether the next patients will be enrolled at the same dose level, or at a lower dose level.

The SMC may have recommended stopping the dose escalation phase after the criterion for MTD (Section 7.1) is fulfilled. Further patients may have been included to confirm this MTD estimate, i.e. to confirm that the EWOC criterion is still fulfilled.

The planned highest dose to be tested in the dose escalation was 4.8mg/kg based upon the pharmacodynamic modeling (refer to Figure 4.1.2.1: 1). Based on the available safety data and the BLRM, exploration of doses higher than 4.8 mg/kg was considered.

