3.3.4.4 Replacement of patients for MTD determination and PK evaluation in phase Ia

Patients who experience a DLT during the MTD evaluation period were not replaced. The following patients without DLT during the MTD evaluation period were considered non-evaluable for MTD determination and were not included in the BLRM analysis:

- Patients who withdrew consent or who were lost from follow-up before completing first two cycles of study treatment.
- Patients who have received less than 70% of the planned BI 905711 doses during first two cycles of study treatment
- Patients who missed 2 or more partial or complete visits during the first two cycles of study treatment.
- Patients with missing PK and evaluation of safety parameters.

These patients were replaced for DLT evaluation during the MTD evaluation period if not decided otherwise by the SMC (e.g. if the number of evaluable patients for the current dose cohort is considered sufficient for a dose escalation decision or MTD determination).

Of note, the dose escalation was determined based on all the safety information of all treated patients including those who were not included in the BLRM analysis.

Page 59 of 165

Proprietary confidential information © 2023 Boehringer Ingelheim International GmbH or one or more of its affiliated companies

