7.3 PLANNED ANALYSES

Analysis of efficacy and safety will be based on the treated set, which will consist of all patients who receive at least one dose of BI 905711.

For the determination of the MTD, only DLT evaluable patients will be considered. Patients will be analyzed according to their starting doses. Any other analysis sets will be defined in the TSAP. No per protocol set will be used in the analysis. However, important protocol violations will be summarised. The TSAP will specify the important protocol violations in detail.

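### SAP 6.3 builds the MTD evaluation set from patients who were not replaced; the protocol requires patients evaluable for DLT, and the two groups can differ

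*SAP*

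**What the plan says.** **Protocol.** Section 7.3: "For the determination of the MTD, only DLT evaluable patients will be considered". Section 3.3.4.4 lists the grounds for non-evaluability: withdrawal or loss to follow-up before two cycles are complete, under 70% of planned dose over two cycles, two or more missed visits, and missing PK and safety evaluations. DLT-free patients meeting any of these "were considered non-evaluable for MTD determination and were not included in the BLRM analysis". Replacement comes in a separate sentence and is conditional: "These patients were replaced for DLT evaluation during the MTD evaluation period if not decided otherwise by the SMC", for instance when enough evaluable patients are already available. Section 3.1.1.3 gives a concrete case. "For further dose-escalation steps (dose level of 0.2 mg/kg and above), four CRC patients were required"; but if only three were evaluable "and none experienced a DLT as defined in Section 5.2.6.1.5 within the MTD evaluation period, then dose escalation occured" on those three.

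**SAP.** Section 6.3 defines the MTD evaluation set (MTDS): "This includes all patients in the TS who were not replaced for the MTD determination". Its operational input is a list of replaced patients: "The list of replaced patients will be provided by the Trial" Clinical Monitor by the last report planning meeting (RPM). Protocol 3.3.4.4 is cited for the replacement rules. Section 7.4.1 runs the BLRM on the MTDS. It presents the DLT count per dose after leaving out patients who stopped in the first cycle for reasons other than a DLT. Section 4 declares no change from the planned analysis.

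**The concern.** Being non-evaluable and being replaced are different states, and the SMC waiver is what separates them. A DLT-free patient who fails an evaluability criterion and is not replaced is outside the protocol's BLRM population. The same patient is inside the SAP's MTDS and contributes a DLT-free observation without having completed the assessment the protocol requires.

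The first-cycle exclusion in SAP 7.4.1 makes this worse, because it matches neither the MTDS nor the two-cycle MTD evaluation period. The MTD and the number of patients with DLTs are the Phase Ia primary endpoints. An undeclared change of analysis set therefore affects the denominator of one and the posterior of the other. Adding DLT-free observations can only lower the posterior DLT rate.

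**Working it through.** **1. Where an unreplaced, DLT-free, non-evaluable patient goes**

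| Patient | Protocol BLRM | SAP BLRM (MTDS) | SAP DLT table |
|---|---|---|---|
| Stopped in cycle 1, no DLT | out | in | out |
| Withdrew in cycle 2 | out: "Patients who withdrew consent or who were lost from follow-up before completing first two cycles of study treatment" | in | in |
| Under 70% of dose, missed visits, or missing PK and safety data | out | in | in |

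**2. Could such patients exist?** Protocol 1.2 reports 48 treated patients (26 CRC, 22 non-CRC) and no DLT. Every cohort from 0.2 mg/kg upward therefore qualified for the three-evaluable rule. The CRC minimums in Table 4.1.2.1:1 add to 1 + 1 + 6×4 = 26, exactly the number treated. If each dose level met its minimum, no CRC replacement was added, and a list of replaced patients would remove no CRC patient from the MTDS.

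**3. Reproducing the protocol's BLRM.** The model is logit(π_d) = log α + β·log(d/3.6), with the three-component prior of Table 7.1: 1 and the posterior obtained by grid integration.
- Prior P(rate ≥ 0.33) at 4.8 mg/kg: 0.339 (protocol 0.338).
- Scenario 12 of Table 10.3: 1, at 0.6 mg/kg with 1 DLT in 4: 0.314 (protocol 0.315).

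**4. Direction of the bias.** In Scenario 12, treat one DLT-free patient at 0.6 mg/kg as non-evaluable. The overdose probability is 0.394 with 1/3 and 0.314 with 1/4. Both exceed 0.25, so this shows direction only.

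**5. Size with the reported data.** With no DLTs the likelihood is the product over doses of (1 − π_d)^n_d. The documents do not give all dose-level sizes, so layouts are built as follows:
- CRC at the minimums: 1, 1, 4, 4, 4, 4, 4, 4.
- Protocol 1.2 gives 8 patients in total at each of 0.6, 1.2 and 2.4 mg/kg, hence 4 non-CRC at each, 12 in all.
- The other 22 − 12 = 10 non-CRC patients go to 0.02 and 0.06 mg/kg (at most 1 each) and to 0.2, 3.6 and 4.8 mg/kg (at most 4 each).
- With none, one or two patients at the two lowest doses there are 6, 20 and 15 arrangements: 6 + 20 + 15 = 41 layouts.

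Reference layout 1, 1, 6, 8, 8, 8, 8, 8 (n = 48), results at 4.8 mg/kg:

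| Patients counted | 97.5% quantile | Mean | P(rate ≥ 0.33) |
|---|---|---|---|
| 48 (all) | 0.104 | 0.023 | 0.00015 |
| 47 (one fewer at 4.8) | 0.109 | 0.024 | 0.00023 |
| 42 (one fewer at each dose from 0.2 up) | 0.116 | 0.026 | 0.00028 |
| 36 (two fewer at each dose from 0.2 up; assumed upper case) | 0.131 | 0.029 | 0.00055 |

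Six is the most the three-evaluable rule yields, one for each four-patient CRC cohort. Across all 41 layouts the quantile is 0.104 to 0.130 with 48 patients and 0.116 to 0.150 with 42. Within a layout the shift is 0.012 to 0.020. The largest overdose probability in any layout, including the 36-patient case, is 0.0039.

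**The case against.** The best defence is that the protocol's set was intended. SAP 6.3 cites protocol 3.3.4.4, which itself bars non-evaluable patients from the BLRM. SAP 5.1 defines the MTD by the BLRM of protocol section 7, which contains the evaluability rule, and SAP 3 assumes familiarity with the protocol. Intent is plausible. But 3.3.4.4 is cited only for replacement, the waiver there is what makes the two groups differ, and the only list requested is of replaced patients.

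The first-cycle exclusion could also be read as qualifying the whole MTD analysis. The BLRM population would still be wrong, because cycle-2 losses, under-dosing and missing assessments stay in.

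It is also fair that no affected patient is shown. The match at 26 is circumstantial: a cohort of three with an extra patient elsewhere gives the same total. The shortest treatment duration in protocol 1.2 is 15 days. Depending on how that was computed, every patient may have had a second dose, and the cycle-1 example would then be empty.

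The size range can be narrowed too. The amendment log mentions an agreement not to backfill non-CRC patients below dose level 3. That leaves 6 layouts, with quantiles of 0.104 to 0.115 (n = 48) and 0.116 to 0.130 (n = 42). The current Table 4.1.2.1:1 still lists one non-CRC patient at each of the two lowest doses, so the wider range is kept. Either range is small.

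The absence of any effect on a decision is accepted in full.

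**Conclusion.** The point holds as a conflict of wording. As written, SAP 6.3 gives a Phase Ia primary analysis set that can differ from the protocol's, without declaring it, and SAP 7.4.1 can give the count table and the BLRM different denominators. Any departure can only make the reported DLT posterior look more favourable.

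The practical size is slight: about 0.005 on the upper quantile at 4.8 mg/kg for one patient at that dose, and 0.012 to 0.020 for six. This rests on the assumed layouts and on non-evaluable patients having existed and gone unreplaced, which the documents neither confirm nor exclude. The EWOC criterion is met by a wide margin either way, the DLT count is zero under both sets, Phase Ia recruitment is complete, and the finding that the MTD was not reached stands. Only denominators and posterior summaries would shift. It should still be corrected, because it concerns primary endpoints and the correction is cheap.

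**What to change.** - **SAP 6.3:** define the MTDS as treated patients who either had a DLT in the MTD evaluation period or meet none of the non-evaluability criteria of protocol 3.3.4.4, whether or not they were replaced. Continue to exclude patients replaced under protocol 5.2.6.1.5 for insufficiently treated nausea, vomiting or diarrhoea.
- **SAP 7.4.1:** use this one set for both the DLT count table and the BLRM, and delete the separate first-cycle exclusion.
- **Last RPM:** document all non-evaluable patients with reasons, in addition to those replaced.

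The cost is two SAP sentences and one listing. The downside is a possibly smaller denominator and slightly wider posterior intervals.
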